1.3.4. Outcomes

1.3.4.1. The mean change in test scores before and after two instructive modules is the primary outcome measurement.

1.3.4.2. GEFT score and self-assessment of satisfaction are the secondary outcome measurements.

1.3.5. Statistical analysis:

Data are analyzed using the SPSS 22.0 software (SPSS Inc., an IBM company, Chicago, IL, USA) and GraphPad Prism 5 software (GraphPad Software, Inc., San Diego, CA, USA). The Kolmogorov-Smirnov test is used to assess the normal distribution of variables. Statistical significance will be determined using the Student *t* test for continuous variables and the Mann-Whitney *U* test or Wilcoxon rank test for skewed variables. Percentage (%) of change ([posttest value - pretest value]/[pretest value] × 100) in multiple-choice test as well as in multimedia situational test. Categorical variables are analyzed using the chi-square test or the Fisher's exact test when sample sizes were small. Two-sided *P* values < 0.05 are considered statistically significant.

Anticipated Works, Outcomes, and Effects

1. Anticipated progression of the study

- 1.1. We will conduct a 2-year study between August 1, 2015 and July 30, 2017. I
- 1.2. n the first year, we plan to establish an M-TEL platform in App format and invite 20 testing personnel (academic physicians in teacher's aspects and junior residents in beginners' aspects) to help developing and verification.
- 1.3. In the second year, we plan to recruit 60 subjects to undergo pretestinstruction-posttest experiments and correlate anthropological characteristics, cognitive style, M-TEL modules, test category, performances, and satisfactions.

2. Anticipated possible problems and resolutions

2.1. Although we investigate the performance of M-TEL by pretest and posttest without any invasive procedure, participants may decline to attend this study due to unfavorable allocation and instruction after randomization. Moreover, we aim to control the age, gender, and GEFT

ratios in the present study. Accordingly, we need more eligible candidates as anticipated. Fortunately, there are approximate 150 UME students in our university each year. However, we need a study assistant to obtain written ICFs and manage our experimental data.

- 2.2. Despite e-learning is useful in many medical education studies, its use is still limited due to deficient resource of mobile technology in UME students, unstable internet connection in Gueishan district of Taoyuan city, and difficulty in executing the M-TEL App software on different mobile devises. In this study, we have to develop a M-TEL platform to simultaneous teaching, interaction, and assessment on tablets and smart phones. We need a team work to overcome this technical problem. Our investigators including academic physicians, expert in web-based learning, and medical technician who have many experiences in preparing instructive materials, teaching UME students, and assessing performance of medical learning. Nevertheless, we need a full-time study assistant to help us to process the computer programming.
- 2.3. In view of the online safety issues involved in handling participants' privacy, the M-TEK will be enabling to protect personal information from hacking. Our need expert helps in maintaining internet security. Otherwise, anonymous using of M-TEL will provide the highest safety but cannot enhance the learners' long-term performance.

3. Anticipated contributions to academic research, national development, and other clinical applications

As mentioned above, the presence of a paucity of ORL-HNS learning in current UME curricula highlight the need to enhance the learning performance inside and outside the classrooms in order to enhance ORL-HNS knowledge and clinical skills for UME students and postgraduate general physicians. This study will set up the important M-TEL platform for self-directed learning. Moreover, identification of personally cognitive style to choose a proper instructional material on the M-TEL platform can reform the ORL-HNS learnings in UME. Finally, the UME students may use the M-TEL anytime and anywhere without significant increasing their cognitive loads and improve learning outcomes.

4. Anticipation of trainings for study researchers

The medical teachers can be familiar with the design of the M-TEL system and increase their ability of handling e-learning to effectively blend instructional design and learning objective principles. The professors of web-based learning can extend researches in the UME level. The computer programmers can train their ability to establish an innovative learning tool to deliver UME education. Modified Protocol (Figure 2): (Add AttrakDiff2 questionnaire; sample size estimation of the validation study) Protocol No.: NSC-105-2511-S-182A-006-IRB No.: 105-5290C

User Experience- the AttrackDiff2

Global satisfaction score is measured using a visual analogue scale from 0 to 10 as mentioned above. For more delicately evaluate the acceptance of technical innovations, we will assess "user experience" using the AttrakDiff2.⁴²

AttrakDiff2 is developed as a tool by Hassenzahl's research group to be able to quantify attractive, identifiable, stimulating, and pragmatic qualities. The tool uses 4x7 anchor scales, in total 28 questions. The anchors are presented in the form of semantic differentials and a 7-point Likert scale is employed for rating the intensity of the items. The poles of each item are opposite adjectives (eg, "confusing-clear", "unusual-ordinary", "good-bad"). Table 4 demonstrate the AttakDiff2. Each of the mean values of an item group creates a scale value for pragmatic quality (PQ), hedonic stimulation (HQ-S), hedonic identification (HQ-I), and attractiveness (ATT).

Attributes in the PQ group describe how easy the user finds it to work with the provided program or environment. Attributes belonging to HQ-S describe factors that encourage the personal growth of users and provide stimulation to give them the opportunity to enhance their knowledge and development. The attributes falling into the HQ-I category make it possible to identify the social impact that using a product can have for users, including the "messages" that are communicated by using the evaluated product. Last, the attributes of the ATT group depict the overall experience a product has to offer to its users, that is, its attractiveness.

Sample Size Estimation of the Validation Study

The sample size for this study has been estimated using the primary outcome effect (change in multiple-choice test scores) among six undergraduate medical students in the system-design study: increased 43±18 [IM module] & 35±21 [PPS module]) in the pilot study. Using a two-tailed Wilcoxon signed-rank test for calculating the sample size (normal parent distribution; effect size, 0.41; type I error, 0.05; power, 80%) using G*Power 3.1.9.2 software, we get a sample size of 26 in each group at the minimum

power of 0.80. For considering an approximate 10% drop-out rate to fulfill the criteria of intention-to-treat analysis, we need at least 30 participants to attend this study. Accordingly, we estimate that a total of 60 participants included in analysis is suitable for the validation study (Part II of the present study). For better characterization and comparison of primary outcome after team discussion, we decide to use "percentage change" in addition to "change" in the future study.

Reference

- Taiwan Medical Accreditation Council. Six-years program of medical education. http://www.heeact.edu.tw/ct.asp?xItem=14388&ctNode=332&mp=3, accessed 6 December 2014.
- American Association of Medical Colleges. Recommendations for clinical skills curricula for undergraduate medical education. Executive summary. Washington, DC: American Association of Medical Colleges; 2005:3.
- Effective Use of Educational Technology in Medical Education. American Association of Medical Colleges (AAMC) Institute for Improving Medical Education. Washington 2007:3.

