This study aims: (1) setup up a M-TEL that can provide instant, interactive, and reliable information; (2) to determine whether M-TEL is an effective tool for the instruction of ORL-HNS; and (3) to compare effects of different cognitive styles on learning outcomes of M-TEL with various modules of medical education.

Importance

- Development of an innovative M-TEL teaching tool of ORL-HNS that have been verified by academic otolaryngologists and junior residents.
- 2. Validation of the novel M-TEL of ORL-HNS in UME students.
- Real understanding of the differences in performance on two elearning modules: text-figure PowerPoint show (PPS) and interactive multimedia (IM) module.
- Better recognition of the differences in performance on two cognitive styles: field dependence and field independence. Reasonable comprehension of the interaction of cognitive style and e-learning modules.
- Critically pedagogical evaluation and improvement of this educational innovation in order to implement this M-TEL in UME curricula to reform the current ORL-HNS education.

Reviews of Literatures

More recently, the smartphone and tablet featuring with faster processors, improved memory, and smaller batteries, can not only provide mobile communication but also advanced functions such app utilities. Embedded elearning in such mobile devices can affect our educational environments. For example, the European Society of Cardiology engaged to develop an e-learning platform to provide a very systematic 360° approach to ensure every participant will have the skills, knowledge, and professional attitude.²¹ Hardyman *et al.*¹⁹ found a high prevalence of iDoc usage in house staffs, a project offering a smartphone library of medical textbooks to medical trainees and concluded that

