1.1. Study design

This study is a prospective, randomized, parallel-controlled, blinded trial that will be conducting from August 1, 2015 to July 31, 2017 at a university (Department of ORL-HNS, School of Medicine, College of Medicine, Chang Gung University, Taoyuan, Taiwan). **Figure 3** shows the study protocol.

[figure not shown]

Figure 3. Block Diagram of the Study Protocol

System-design study (n = 20; 10 academic physicians and 10 junior residents) in which an e-learning platform of emergent ORL-HNS disorders with translating into an App that is executable on the mobile device will be designed. (A) Instructions of the most common 10 emergent ORL-HNS disorders according to our previously unpublished data will be collected. (B) Two different e-learning modules (visual-auditory text-figure PPS or an IM) will be established. (C) The App software of two e-learning modules will be programmed; and (D) Tests including a multiple-choice test and a multimedia situational test assessment will be set. The participants will assist our developing, evaluating, and improving the e-learning instruction.

Validation study will be performed on 60 UME subjects without previous

ORL-HNS training by pretest-posttest and self-assessment of satisfaction using the randomly assigned M-TEL instructions. Prior to the validation study, all participants will be assessed by the GEFT test for determination of their cognitive style (field dependence or field independence). The flowchart diagram following the CONSORT 2010 guideline demonstrated our study design (**Figure 4**).³⁵

[figure not shown]

Figure 4. CONSORT Flowchart of the Validation Study

After randomization, students are instructed on two modules of emergent ORL-HNS disorders, using either a PPS or an IM module. Subjects are evaluated on emergent ORL-HNS disorders using a text-based assessment (multiple-choice test) and a multimedia assessment (situational test) take place prior to and following instruction. Self-reported satisfaction with the study materials by the participants was obtained after examination. The interactions

of field dependence/independence, PPS/IM, and learners' satisfaction will be investigated in order to improve the preliminary version of M-TEL.

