1.2.4. Test Setup

Figure 7 demonstrates the Kirkpatrick's four levels of evaluation include: level 1, reactions; level 2, learning; level 3, transfer; and level 4, results.³⁷ We will set three multidimensional evaluations in our validation study: self-assessment of satisfaction (level 1), multiple-choice test (level 2), and multimedia situational test (level 3). The guest investigators will answer the multiple-choice test and multimedia situational test to improve the questions.

- 1.2.4.1. Multiple-choice test: Questions are obtained from previously developed examinations of emergent ORL-HNS disorders and undergraduate final examinations. Questions that are not adequately addressed in both self-study materials were removed. Then a nine-question multiple-choice test will be set. The test is then uploaded onto the M-TEL platform such that students can answer online and submit the test once completed.
- 1.2.4.2. Multimedia situational test: Virtual patient cases with specific emergent ORL-HNS disorders are newly developed. Situational questions that are not adequately addressed in both self-study materials were removed. Then a multiple-choice test with nine situational questions will be set. The test is then uploaded onto the M-TEL platform such that students can answer online and submit the test once completed.

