1.3. Validation study (the second year)

1.3.1. Participants

For the relative small sample size of the present study, we analyzed all variables using non-parametric approaches. The sample size for this study was estimated using the primary outcome effects (mean posttest score) in two previously published studies.^{12,30} Using a two-tailed Wilcoxon signed-rank test for calculating the sample size (normal parent distribution; effect size, 0.8; type I error, 0.05; power, 80%), we got a sample size of 27 in each group at the minimum power of 0.80. For considering a 10% drop-out rate to fulfill the criteria of intention-to-treat analysis, we needed at least 30 participants to attend this study.

1.3.1.1. The **inclusion criteria** of the present study are:

- 1) Age > 20 years old & < 70 years.
- 2) UME students (defined as the 5 or 6 years of medical school training).

1.3.1.2. The exclusion criteria are:

- 1) Previous ORL-HNS training;
- 2) Declining to participate.

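### Section 1.3.5 neither uses the GEFT strata nor names a method for the style-by-module interaction; the main comparison stays valid, and the repair is cheap

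*Combined protocol and SAP*

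**What the plan says.** - **Aims.** Under Objectives, the third of three unranked aims is "to compare effects of different cognitive styles on learning outcomes of M-TEL with various modules of medical education". The Importance list adds, as an expected benefit, "Reasonable comprehension of the interaction of cognitive style and e-learning modules".
- **Design.** Section 1.1 says that the interactions "of field dependence/independence, PPS/IM, and learners' satisfaction will be investigated in order to improve the preliminary version of M-TEL". This is the only place that commits to examining interactions, and the outcome it names is satisfaction.
- **GEFT.** Section 1.1 states: "Prior to the validation study, all participants will be assessed by the GEFT test for determination of their cognitive style". Section 1.3.2 makes the resulting category (score of 12 or below, or above 12, per section 1.3.3) the stratification factor, with 1:1 allocation in each stratum.
- **Outcomes.** Section 1.3.4 makes change in test scores primary and adds that "GEFT score and self-assessment of satisfaction are the secondary outcome measurements".
- **Analysis.** Section 1.3.5 names a Kolmogorov-Smirnov check, the Student t test, the Mann-Whitney or Wilcoxon test, the chi-square or Fisher test, and a percentage-change formula. Section 1.3.1 says instead that "we analyzed all variables using non-parametric approaches".
- **Elsewhere.** Item 1.3 of the anticipated progression says that style, modules, performance and satisfaction will be correlated, without giving a method. The Modified Protocol adds the AttrakDiff2 questionnaire, a new sample-size estimate and percentage change, but no interaction analysis.

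**The concern.** The trial measures cognitive style, stratifies on it and says it will look at how style and module combine, but the analysis section does not follow through. A test of field-dependent against field-independent students is possible with the listed methods and would answer part of aim 3. It would not show whether the IM-PPS difference varies by style. With no method named, the contrast, the model and the outcome could all be settled once results are known.

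Two things are at stake. First, a style-specific finding could be read as firmer than a trial of 60 can make it, and the plan does not warn how imprecise it will be. Second, precision may be given away in the main comparison, because the strata and the pretest are available and unused.

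Listing GEFT as an outcome is a smaller matter. It is measured before instruction and is nowhere said to be repeated, so the module cannot affect it.

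**Working it through.** **Inputs.** From the Modified Protocol's sample-size section: pilot change in multiple-choice score 43 (SD 18) with IM and 35 (SD 21) with PPS, among six students; planned total 60. From section 1.3.5: two-sided 5% level. Not in the documents, so assumed: the style split, the pre-post correlation, and the share of variance explained by the stratum.

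**The plan's own effect size.** Pooled SD = √((18² + 21²)/2) = 19.56, and 8/19.56 = 0.41, which matches the stated value. That calculation concerns the module comparison; no sample size or power is given for the interaction.

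**Interaction precision.** The interaction is the IM-PPS difference in one style minus that in the other. With n₁ and n₂ students per arm in the two strata, SE = 19.56 × √(2/n₁ + 2/n₂), and the 95% half-width is 2.003 × SE (t on 56 df).

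| Style split | Per arm | SE (SD units) | Half-width (points) | Power, 8-point interaction |
|---|---|---|---|---|
| 50:50 | 15, 15 | 0.516 | 20.2 | 12% |
| 30:70 | 9, 21 | 0.563 | 22.1 | 11% |
| 20:80 | 6, 24 | 0.645 | 25.3 | 10% |

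Power is from the noncentral t distribution. Eight points equals the whole pilot difference between modules and is only illustrative. At the even split, power is 7% for 4 points and 34% for 16.

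**Uncertainty in the SD.** The number of pilot students per module is not stated. The 95% limits are 19.56 × √(df/χ²).
- Three per module, 4 df: SD 11.7 to 56.2, half-width about 12 to 58 points, power for 8 points 26% down to 6%.
- Six independent students per module, 10 df: SD 13.7 to 34.3, half-width about 14 to 36 points, power 20% down to 7%.

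These figures concern multiple-choice score change. The documents give no variability for satisfaction or for the situational test.

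**Pretest adjustment.** With equal pretest and posttest SDs and correlation ρ, adjusting change for pretest multiplies the variance by (1 + ρ)/2. For ρ = 0.3, 0.5 and 0.7 the SE is multiplied by 0.806, 0.866 and 0.922, a cut of 19, 13 or 8%. The even-split half-width of 20.23 becomes 16.3, 17.5 or 18.7 points.

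**Ignoring the strata in the main test.** If the stratum explains a share R² of the variance in change, the unstratified SE is too large by 1/√(1 − R²) − 1, and the actual type I error is 2(1 − Φ(1.96/√(1 − R²))). For R² = 0, 10 and 20% the SE is 0, 5.4 and 11.8% too large and the error rate is 5.0, 3.9 and 2.8%. A simulation with a one-SD stratum effect and 15 per cell (R² = 0.25/1.25 = 20%) gave about 2.9%, in agreement.

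**Within-style tests as a substitute.** If the true effect is 0.41 SD in both styles, power within each style at 15 per arm is 0.192. Exactly one style is then significant with probability 2 × 0.192 × 0.808 = 0.31, although no interaction exists.

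**Multiplicity.** Two test scores and satisfaction give three interaction terms: 1 − 0.95³ = 14% chance of at least one false positive under independence. Adding the four AttrakDiff2 scales makes seven: 1 − 0.95⁷ = 30%.

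**The case against.** The best defence is that little was promised and nothing central is harmed. The Importance list states a hoped-for benefit, aim 3 can be read as a comparison of styles, and the one explicit commitment names satisfaction and may use the word interactions loosely. The listed two-group tests are legitimate for IM versus PPS. Pretest adjustment corrects no error, and a linear model sits awkwardly with the statement in section 1.3.1 that "we analyzed all variables using non-parametric approaches".

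Much of this stands. Applying the interaction to score change is an inference from aim 3 and section 1.1 together, and the model is a gain in precision, not the repair of a bias. What does not fall away is that the strata are built into the randomisation and absent from the analysis, and that the commitment in section 1.1 has no method on any reading.

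Some stronger readings are tempting but unsupported:
- **The main result is invalid because the strata are ignored.** No: the test becomes conservative, and only if the stratum predicts score change.
- **Separate tests within each style are planned.** The documents do not say so; the 31% figure shows only why they should not stand in for an interaction test.
- **Teaching material will be assigned by style.** The section on anticipated contributions presents matching as a possible future benefit, not as a rule of this trial.
- **Twenty points can be turned into a number of questions.** Each test has nine questions ("Then a nine-question multiple-choice test will be set"; "Then a multiple-choice test with nine situational questions will be set"), but the scoring scale is not stated. With percent-correct scoring and three students per module, mean change moves in steps of 100/27 = 3.7 points (33.3, 37.0, 40.7, 44.4), so neither 43 nor 35 could arise. Six per module could give both: 23/54 = 42.6 and 19/54 = 35.2. The conversion is therefore not made here.

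**Conclusion.** The point holds as an omission in the analysis plan. Section 1.3.5 does not use the GEFT strata and has no method for the interaction that section 1.1 says will be investigated. For score change, the interaction would be known only to within about 20 points at an even split or 25 at 20:80. Taking the uncertainty of the pilot SD into account at an even split, the half-width could be anywhere from about 12 to 58 points (4 df) or 14 to 36 (10 df). Those figures rest on an assumed style split and on a pilot of unstated size per module; none is available for satisfaction. In every case shown, power for an 8-point interaction is at most 26%, so the result can only be exploratory. The GEFT outcome label is clerical. Overall this is a cheap improvement, at the low end of what should be changed.

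**What to change.** 1. For each of the two tests, compare change in score between modules in a linear model with GEFT stratum and pretest score, presented as an improvement in precision. Give a stratified rank test in support, and reconcile sections 1.3.1 and 1.3.5 on parametric versus non-parametric methods.
2. For aim 3 and the commitment in section 1.1, add a module-by-GEFT term to the model for each test score and to a model for satisfaction. The satisfaction model has no pretest term, because satisfaction is recorded only after instruction. Report each interaction estimate with its 95% confidence interval as exploratory, state the expected precision, and say whether the four AttrakDiff2 scales are included.
3. State that no style-specific conclusion will be drawn from separate within-style p-values or from a single nominal p below 0.05, and that style matching is hypothesis-generating.
4. List GEFT as a baseline stratification factor and remove it from the outcomes.

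The cost is slightly more analysis work on variables already collected, with no new participants or data. The sponsor gives up only the option of presenting the style-by-module result as more than exploratory.

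### No planned analysis of the primary outcome uses the pretest or the randomisation stratum as a covariate, and percentage change is added without a stated role or a rule for a zero pretest

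*Combined protocol and SAP*

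**What the plan says.** - Primary outcome (Section 1.3.4.1): "The mean change in test scores before and after two instructive modules is the primary outcome measurement". The section does not say which of the two tests is meant.
- Sizing (Modified Protocol, Sample Size Estimation of the Validation Study): based on the "primary outcome effect (change in multiple-choice test scores) among six undergraduate medical students in the system-design study", given as "increased 43±18 [IM module] & 35±21 [PPS module".
- Tests (Section 1.3.5): the Student t test, the Mann-Whitney U "test or Wilcoxon rank test for skewed variables", and chi-square or Fisher for categories. No regression or covariance model is listed. Section 1.3.1 adds: "For the relative small sample size of the present study, we analyzed all variables using non-parametric approaches".
- Percentage change (Section 1.3.5): "Percentage (%) of change ([posttest value - pretest value]/[pretest value] × 100) in multiple-choice test as well as in multimedia situational test". The sentence gives a formula but no role, test or rule for a zero denominator. The Modified Protocol then says "we decide to use 'percentage change' in addition to 'change' in the future study", to characterise and compare the primary outcome better.
- Data available: Section 1.3.2 stratifies randomisation by field dependence or independence and has all students take both tests before and after instruction. On test length, Section 1.2.4.1 says: "Then a nine-question multiple-choice test will be set". The situational test also has nine questions. Students with earlier ORL-HNS training are excluded.

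**The concern.** There are two linked gaps, the first the more useful to close.

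**Unused baseline information.** The pretest enters the planned analysis only by subtraction or as a denominator. Subtraction fixes its coefficient at 1. A covariance model estimates that coefficient and usually gives a narrower interval for the module difference. The stratum used in randomisation is also left out of the comparison. With 60 students and a pilot effect of 0.41, precision is scarce, and both variables are already collected.

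**An added scale with no stated role.** Percentage change divides by the pretest. A student with 0 of 9 correct has no value, and the plan does not say what happens to that student. The scale also depends on the starting score: a gain of four questions is +400% from 1/9 but +80% from 5/9. If raw and percentage change are both tested at 0.05, a module effect could be claimed on either.

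**Working it through.** **1. The plan's own figures.** The pilot changes are read as percentage points, since a nine-item score cannot rise by 43 items. Pooled SD = √((18² + 21²)/2) = 19.56, and d = (43 − 35)/19.56 = 0.409, which matches the stated 0.41. The stated 26 per group is half of the 52 that a two-tailed one-sample signed-rank test needs at d = 0.409. A between-group Mann-Whitney test would need 99-100 per group. That is a separate problem, but it means the trial starts from low power.

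**2. Raw change, 30 per arm.** Noncentral t, d = 0.41, 58 df: power 34.5%. The 95% CI half-width is 2.002 × 19.56 × √(2/30) = 10.1 points.

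**3. ANCOVA with pretest and stratum.** Assume equal pretest and posttest SD and pre-post correlation r, with no extra gain from the stratum. The variance of the ANCOVA estimate relative to raw change is (1 + r)/2, so the effective d is 0.41/√((1 + r)/2), with 60 − 4 = 56 df.

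| r (assumed) | Variance ratio | Effective d | Power | CI half-width |
|---|---|---|---|---|
| raw change | 1.00 | 0.410 | 34.5% | 10.1 |
| 0.8 | 0.90 | 0.432 | 37.7% | 9.6 |
| 0.5 | 0.75 | 0.473 | 43.7% | 8.8 |

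More generally the ratio is 1 − c², where c is the correlation of pretest with change: 1.00 at c = 0, 0.91 at c = −0.3, 0.75 at c = −0.5. Under equal SDs, c = −√((1 − r)/2). Hence r = 0.5 corresponds to c = −0.5, and r = 0.8 to c = −0.32 with a pretest SD of 19.56/√0.4 = 31 points, which is wide for this test.

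**4. Simulation on nine-item scores.** Pilot change, scores rounded and cut to 0-9, assumed pretest mean 30-50 and SD 10-20, c from −0.5 to +0.3 (36 settings, 1000 replicates each). ANCOVA power minus raw-change t-test power ran from −1 to +17 percentage points. Under the null (9 settings, 5000 replicates), ANCOVA with pretest and stratum had type I error 4.9-5.4%.

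**5. Zero pretests.** P(0 of 9) = (1 − p)⁹, with p the assumed per-item success; P(at least one among 60) = 1 − (1 − P(0))⁶⁰.

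| p (assumed) | P(0 of 9) | Expected in 60 | At least one in 60 |
|---|---|---|---|
| 0.25 | 7.5% | 4.5 | 99% |
| 0.35 | 2.1% | 1.2 | 72% |
| 0.50 | 0.2% | 0.1 | 11% |

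**6. Testing both scales.** On the multiple-choice score alone, simulated false-positive rates for any P < 0.05 were about 7-8%, with 5-9% across the wider set of assumptions. Two independent tests would give 1 − 0.95² = 9.75%. In a simulation of the pilot effect (zero pretests dropped, assumed pretest mean 30-50 and r 0.3-0.5), the two scales gave different significance verdicts in 11-22% of trials.

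**The case against.** The strongest reply is that nothing here is invalid. A between-group comparison of change is unbiased under randomisation, Section 1.3.1 chose non-parametric methods because the sample is small, and ANCOVA puts a linear model on a nine-item score. All of that stands. A reader might infer that the planned primary analysis is biased; the documents do not support that. Against the last point, Section 1.3.5 itself admits the t test, and the simulated type I error of the ANCOVA is close to 5%.

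A reader might also infer that percentage change is a second primary outcome. The text does not go that far. Section 1.3.4.1 names one primary measure, percentage change is absent from the list of outcomes, and the Modified Protocol sizes on change. Its addition can be read as supplementary, and the reference to a future study is loose, though it closes the paragraph that sizes the validation study. What remains is that its role is not stated.

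Two larger numbers are tempting. Across both tests, the chance of some false positive with both scales is about 12-16%, but raw change alone on the two tests already gives 8-10%, so most of the excess comes from having two tests. And at r = 0.2 ANCOVA would reach 52% power, but that implies c = −0.63, outside the range simulated above, so it should not be relied on.

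Finally, Section 1.1 says that interactions of cognitive style and module will be investigated. It names no method, and it does not put the stratum or the pretest into the primary comparison.

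**Conclusion.** The point holds as a matter of precision and clarity, not bias. The plan leaves out two variables that it already collects. Using them would plausibly lift power from about 35% to 38-44% (r from 0.8 to 0.5, equal SDs, d = 0.41, 30 per arm) and narrow the interval from 10.1 to between 9.6 and 8.8 points. The gain is nil if change is unrelated to pretest, and no setting considered brings 60 students to 80% power.

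The unstated role of percentage change is the lesser point. If it is tested beside raw change on the multiple-choice score, the false-positive rate goes from 5% to about 7-8%. Whether zero pretests occur depends on item difficulty, which the documents do not give: the chance of at least one runs from 11% to 99%. The missing rule and the dependence on the starting score do not rest on any assumption.

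This should be fixed. Confidence is medium, because the pretest mean, SD and pre-post correlation are unknown and the pilot had six students.

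**What to change.** Revise Section 1.3.5 and the closing sentences of the Modified Protocol's sample size section as follows.

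- **Primary analysis:** ANCOVA of the posttest multiple-choice score on module, with the pretest score and the field-dependence stratum as covariates, reported as the adjusted difference in score points with a 95% CI. Once the pretest is in the model, the module coefficient is the same whether the outcome is posttest or change. The model therefore also fits Section 1.3.1, which calls the primary outcome the mean posttest score; the naming should still be made consistent.
- **Supporting outcome:** the situational test, analysed the same way.
- **Sensitivity analysis:** the rank-based comparison of raw change, in line with Section 1.3.1.
- **Percentage change:** descriptive only, without a significance test, with the number of zero pretests reported by arm.

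The cost is wording. SPSS fits the model, and no further data or students are needed. The downsides are a departure from the stated non-parametric approach, the loss of a test on percentage gain, and a benefit that may turn out small.
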